#### Events NOT meeting definition of an AE include:

- Any clinically significant abnormal laboratory findings or other abnormal safety assessments which are associated with the underlying disease, unless judged by the

investigator to be more severe than expected for the subject's condition.

- The disease/disorder being studied or expected progression, signs, or symptoms of the disease/disorder being studied, unless more severe than expected for the subject's condition.
- Medical or surgical procedure (e.g., endoscopy, appendectomy): the condition that leads to the procedure is an AE.
- Situations where an untoward medical occurrence did not occur (social and/or convenience admission to a hospital).
- Anticipated day-to-day fluctuations of pre-existing disease(s) or condition(s) present or detected at the start of the study that do not worsen.

### **12.3.2. Definition of Serious Adverse Events**

If an event is not an AE per definition above, then it cannot be an SAE even if serious conditions are met (e.g., hospitalization for signs/symptoms of the disease under study, death due to progression of disease, etc).

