### 5.4.3. Safety Related Study Specific Dose Adjustment Criteria

If AEs are of severe intensity and are similar across subjects, or if unacceptable pharmacological effects, reasonably attributable in the opinion of the investigator to dosing with GSK2646264, or if dose limiting toxicity (see Section 5.4.1), are observed in at least 2 subjects, relevant reporting and discussion with the GSK medical monitor and the SRT will take place.

If a Serious Adverse Event (SAE) occurs in 1 subject and is deemed to be drug related, this would be deemed an SAR (Serious Adverse Reaction), and dosing will be halted in the individual (Relevant reporting and discussion with the GSK medical monitor and the SRT will take place, and halting of dosing will be considered for all study subjects). If dosing is halted for the entire study, any resumption of dosing will only take place after consideration by the SRT and discussion with the investigators and may necessitate approval of a substantial amendment submitted to the Ethics committees and Regulatory authorities.

[figure not shown]
If average predicted or observed  $C_{max}$  or  $AUC(0-24\text{ h}$  after last dose) of GSK264624 is greater than 16 ng/mL or 220 ng.hr/mL, respectively, subsequent doses may be adjusted based on toxicology cover and this will be agreed by the SRT.

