#### **7.4.1.5. Disease-Related Events and/or Disease-Related Outcomes Not Qualifying as SAEs**

The following disease related events (DREs) are common in subjects with CLE or SLE and can be serious/life threatening:

- Exacerbation of SLE or transformation of CLE into SLE with organ involvement other than the skin

Because these events are typically associated with the disease under study, they will not be reported according to the standard process for expedited reporting of SAEs to GSK (even though the event may meet the definition of a SAE). These events will be recorded on the DRE page in the subject's CRF within the appropriate time frame *agreed upon by the SRT* for completion of DRE CRF pages. These DREs will be monitored by the SRT (see Section 10.8) on a routine basis.

*NOTE: However, if either of the following conditions apply, then the event must be recorded and reported as an SAE (instead of a DRE):*

- *The event is, in the investigator's opinion, of greater intensity, frequency, or duration than expected for the individual subject, or*
- *The investigator considers that there is a reasonable possibility that the event was related to treatment with the investigational product*

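### Appendix 3 and Section 7.4.1.5 classify a serious, possibly drug-related lupus event in opposite ways, and Appendix 3 is ambiguous for skin-only worsening

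*Protocol*

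**What the plan says.** Protocol Section 7.4.1 sends sites to Section 12.3 (Appendix 3) for the definitions of AE and SAE.

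- **Section 12.3.1, events that are not AEs:** "The disease/disorder being studied or expected progression, signs, or symptoms of the disease/disorder being studied, unless more severe than expected" for the subject's condition. Relation to treatment is not mentioned.
- **Section 12.3.2**, of an event outside the AE definition: "it cannot be an SAE even if serious conditions are met (e.g., hospitalization for signs/symptoms of the disease under study"). Its second example is death from progression of the disease.
- **Section 7.4.1.5** defines one class of disease-related event (DRE): "Exacerbation of SLE or transformation of CLE into SLE with organ involvement other than the skin". These go on a separate CRF page and stay out of standard expedited SAE reporting. There are two alternative exceptions. One is intensity, frequency or duration beyond what is expected for the subject. The other is: "The investigator considers that there is a reasonable possibility that the event was related to treatment with the investigational product". If either applies, "then the event must be recorded and reported as an SAE (instead of a DRE").
- **Section 5.4.3:** "If a Serious Adverse Event (SAE) occurs in 1 subject and is deemed to be drug related, this would be deemed an SAR". Dosing then stops in that subject, the Safety Review Team (SRT) discusses the case, and a halt for all subjects is considered.

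AE reporting is part of the primary endpoint (Protocol Section 3). SAP Section 7.1.1 and Appendix 8 plan tables and listings of AEs and SAEs. They contain no DRE table or listing.

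**The concern.** Two current sections answer the same classification question differently, and neither states which prevails. The definitions section tests severity only. The DRE section treats a possible link to treatment as sufficient by itself. A site that goes to the definitions, as Section 7.4.1 directs, can reach a different answer from one that goes to 7.4.1.5.

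Three things depend on the answer:

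- whether the event enters the AE and SAE displays, which carry part of the primary endpoint;
- whether it is reported within 24 hours as an SAE (Section 7.4.1.1) or on a DRE timetable agreed by the SRT (Section 7.4.1.5);
- whether the single-event rule in Section 5.4.3 applies.

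**Working it through.** This is mainly a comparison of texts. The table takes events that meet a seriousness criterion and reads the Section 12.3.1 exclusion literally.

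| Event | Exclusion in 12.3.1 with 12.3.2 | Section 7.4.1.5 | Result |
|---|---|---|---|
| Systemic, more severe than expected | Can be AE and SAE | SAE | Agree |
| Systemic, as expected, unrelated | Not an AE | DRE page | Compatible |
| Systemic, as expected, possibly related | Not an AE, so not an SAE | SAE | Opposite |
| Systemic, expected severity but more frequent or longer than expected | Not an AE, if severity means intensity only | SAE | Opposite on that reading |
| Skin-only, as expected, possibly related | Exclusion says not an AE; other 12.3.1 text says AE | Not covered | Ambiguous |

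**Does the exclusion reach systemic lupus?** The study disease is cutaneous lupus. However, 7.4.1.5 describes the listed systemic events as typically associated with the disease under study, and the 12.3.2 examples include death from progression. A site could reasonably apply the exclusion to them. Section 7.4.1.5 also accepts that a DRE may satisfy the SAE definition, which 12.3.2 denies for anything the exclusion covers.

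**Skin-only worsening.** Section 12.3.1 first defines an AE to include an exacerbated disease, then lists exacerbation of a chronic pre-existing condition as an AE, and afterwards excludes the disease under study. No text settles which prevails. RCLASI components are recorded for lesions (Protocol Section 7.3), and SAP Section 11.2.1 places local tolerability and efficacy at skin-site level. A flare away from the study sites would not be expected in those data.

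**Size of one event.** The inputs are the flat Beta(1,1) prior and the planned 15 Group B subjects (Protocol Section 9.2.1). With x events in n subjects the posterior is Beta(1 + x, 1 + n − x).

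- x = 1: Beta(2, 15), 95% limits 0.016 to 0.302. The protocol gives 0.02 to 0.30, so its figure is reproduced.
- x = 0: Beta(1, 16), upper limit 1 − 0.025^(1/16) = 0.206. The protocol gives 21%, also reproduced.

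Recording 0 of 15 instead of 1 of 15 lowers the upper limit by 0.302 − 0.206 = 0.096, about 10 percentage points. This is the effect of losing any one event. It says nothing about how likely this wording is to lose one.

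**The case against.** The strongest reply is that the study-specific text already settles the systemic case. Section 7.4.1.5 is mandatory, so a site that follows it reports the SAE and Section 5.4.3 applies. Exclusion criterion 6 also keeps out active SLE and significant disease in other organs. A new transformation to SLE could then be called a newly diagnosed condition, which 12.3.1 counts as an AE, or more severe than expected for that subject.

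There are other safeguards:

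- The SRT routinely monitors DREs and reviews unblinded safety data in-stream (Sections 7.4.1.5 and 10.8).
- Section 5.4.3 also sends unacceptable pharmacological effects attributed to dosing, seen in at least two subjects, to the SRT without requiring an SAE.
- The SLE clinical assessment and the follow-up physical examination could reveal worsening.

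Much of this stands. It makes loss of an event possible, not certain. It does not supply a rule of precedence. Monitoring by the SRT does not give an event the SAE classification on which the one-subject rule depends. The SAP has no display for DREs, the SLE assessment or the physical examination.

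A reader might infer that a drug-related skin flare of ordinary severity is simply not an AE. The documents do not support that, because the exacerbation text in 12.3.1 points the other way. A reader might also infer that the definitions necessarily remove these events from the counts. They do so only if a site follows Appendix 3 in preference to 7.4.1.5.

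**Conclusion.** The inconsistency is real and lies in current text. For a serious, possibly drug-related systemic lupus event of expected severity, Appendix 3 and Section 7.4.1.5 give opposite classifications. This rests on treating such an event as part of, or progression of, the disease under study, which 7.4.1.5 itself suggests. For skin-only worsening there is no conflict with 7.4.1.5, which does not cover it; the problem is ambiguity within Section 12.3.1.

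The consequence is conditional. A site relying on Appendix 3 could leave such an event out of the AE and SAE tables and not trigger the one-event rule. One event is enough to matter for that rule. The documents give no basis for estimating how often this would happen.

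It would go too far to call drug-provoked lupus worsening an identified central risk of this product, since the risk table in Section 4.6.1 does not list it. The case for change is that a reporting rule feeding the primary endpoint should give one answer.

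**What to change.** Reconcile Protocol Sections 12.3.1, 12.3.2 and 7.4.1.5 so that a single test covers cutaneous and systemic disease events and states explicitly how treatment-related ones are classified. The test should also settle whether severity alone counts, or intensity, frequency and duration. Cross-refer 12.3.2 to 7.4.1.5, and make clear how the exacerbation text in 12.3.1 relates to the disease-under-study exclusion. The classification feeds the dosing rule in Section 5.4.3, so the sponsor must choose the test; this review does not propose one.

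Add a DRE listing to SAP Appendix 8, so that events recorded by that route appear in the planned safety outputs.

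The cost is protocol wording and one listing. Depending on the test chosen, a few more disease flares may be reported as AEs or SAEs.

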**Serious Adverse Event (SAE) is defined as any untoward medical occurrence that, at any dose:**

**a. Results in death**

**b. Is life-threatening**

NOTE:

The term 'life-threatening' in the definition of 'serious' refers to an event in which the subject was at risk of death at the time of the event. It does not refer to an event, which hypothetically might have caused death, if it were more severe.

**c. Requires hospitalization or prolongation of existing hospitalization**

NOTE:

- In general, hospitalization signifies that the subject has been detained (usually involving at least an overnight stay) at the hospital or emergency ward for observation and/or treatment that would not have been appropriate in the physician's office or out-patient setting. Complications that occur during hospitalization are AEs. If a complication prolongs hospitalization or fulfills any other serious criteria, the event is serious. When in doubt as to whether "hospitalization" occurred or was necessary, the AE should be considered serious.
- Hospitalization for elective treatment of a pre-existing condition that did not worsen from baseline is not considered an AE.

**d. Results in disability/incapacity**

NOTE:

- The term disability means a substantial disruption of a person's ability to conduct normal life functions.
- This definition is not intended to include experiences of relatively minor medical significance such as uncomplicated headache, nausea, vomiting, diarrhea, influenza, and accidental trauma (e.g. sprained ankle) which may interfere or prevent everyday life functions but do not constitute a substantial disruption

**e. Is a congenital anomaly/birth defect****f. Other situations:**

- Medical or scientific judgment should be exercised in deciding whether reporting is appropriate in other situations, such as important medical events that may not be immediately life-threatening or result in death or hospitalization but may jeopardize the subject or may require medical or surgical intervention to prevent one of the other outcomes listed in the above definition. These should also be considered serious.
- Examples of such events are invasive or malignant cancers, intensive treatment in an emergency room or at home for allergic bronchospasm, blood dyscrasias or convulsions that do not result in hospitalization, or development of drug dependency or drug abuse

**g. Is associated with liver injury and impaired liver function defined as:**

- ALT  $\geq$  3xULN and total bilirubin\*  $\geq$  2xULN ( $>35\%$  direct), **or**
- ALT  $\geq$  3xULN and INR \*\*  $> 1.5$ .

\* Serum bilirubin fractionation should be performed if testing is available; if unavailable, measure urinary bilirubin via dipstick. If fractionation is unavailable and ALT  $\geq$  3xULN and total bilirubin  $\geq$  2xULN, then the event is still to be reported as an SAE.

\*\* INR testing not required per protocol and the threshold value does not apply to subjects receiving anticoagulants. If INR measurement is obtained, the value is to be recorded on the SAE form.

- Refer to Section [12.2](#) for the required liver chemistry follow-up instructions

### 12.3.3. Definition of Cardiovascular Events

#### **Cardiovascular Events (CV) Definition:**

Investigators will be required to fill out the specific CV event page of the CRF for the following AEs and SAEs:

- Myocardial infarction/unstable angina
- Congestive heart failure
- Arrhythmias
- Valvulopathy
- Pulmonary hypertension
- Cerebrovascular events/stroke and transient ischemic attack
- Peripheral arterial thromboembolism
- Deep venous thrombosis/pulmonary embolism
- Revascularization

### 12.3.4. Recording of AEs and SAEs

#### **AEs and SAE Recording:**

- When an AE/SAE occurs, it is the responsibility of the investigator to review all documentation (e.g., hospital progress notes, laboratory, and diagnostics reports) relative to the event.
- The investigator will then record all relevant information regarding an AE/SAE in the CRF
- It is **not** acceptable for the investigator to send photocopies of the subject's medical records to GSK in lieu of completion of the GSK, AE/SAE CRF page.
- There may be instances when copies of medical records for certain cases are requested by GSK. In this instance, all subject identifiers, with the exception of the subject number, will be blinded on the copies of the medical records prior to submission of to GSK.
- The investigator will attempt to establish a diagnosis of the event based on signs, symptoms, and/or other clinical information. In such cases, the diagnosis will be documented as the AE/SAE and not the individual signs/symptoms.
- Subject-completed Value Evidence and Outcomes questionnaires and the collection of AE data are independent components of the study.
- Responses to each question in the Value Evidence and Outcomes questionnaire will be treated in accordance with standard scoring and statistical procedures detailed by the scale's developer.
- The use of a single question from a multidimensional health survey to designate a

cause-effect relationship to an AE is inappropriate.

### 12.3.5. Evaluating AEs and SAEs

#### Assessment of Intensity

The investigator will make an assessment of intensity for each AE and SAE reported during the study and will assign it to one of the following categories:

- Mild: An event that is easily tolerated by the subject, causing minimal discomfort and not interfering with everyday activities.
- Moderate: An event that is sufficiently discomforting to interfere with normal everyday activities
- Severe: An event that prevents normal everyday activities. - an AE that is assessed as severe will not be confused with an SAE. Severity is a category utilized for rating the intensity of an event; and both AEs and SAEs can be assessed as severe.
- An event is defined as 'serious' when it meets at least one of the pre-defined outcomes as described in the definition of an SAE.

#### Assessment of Causality

- The investigator is obligated to assess the relationship between study treatment and the occurrence of each AE/SAE.
- A "reasonable possibility" is meant to convey that there are facts/evidence or arguments to suggest a causal relationship, rather than a relationship cannot be ruled out.
- The investigator will use clinical judgment to determine the relationship.
- Alternative causes, such as natural history of the underlying diseases, concomitant therapy, other risk factors, and the temporal relationship of the event to the study treatment will be considered and investigated.
- The investigator will also consult the Investigator Brochure and/or Product Information, for marketed products, in the determination of his/her assessment.
- For each AE/SAE the investigator **must** document in the medical notes that he/she has reviewed the AE/SAE and has provided an assessment of causality.
- There may be situations when an SAE has occurred and the investigator has minimal information to include in the initial report to GSK. However, **it is very important that the investigator always make an assessment of causality for every event prior to the initial transmission of the SAE data to GSK.**
- The investigator may change his/her opinion of causality in light of follow-up information, amending the SAE data collection tool accordingly.
- The causality assessment is one of the criteria used when determining regulatory

reporting requirements.

### Follow-up of AEs and SAEs

- The investigator is obligated to perform or arrange for the conduct of supplemental measurements and/or evaluations as may be indicated or as requested by GSK to elucidate as fully as possible the nature and/or causality of the AE or SAE.
- The investigator is obligated to assist. This may include additional laboratory tests or investigations, histopathological examinations or consultation with other health care professionals.
- If a subject dies during participation in the study or during a recognized follow-up period, the investigator will provide GSK with a copy of any post-mortem findings, including histopathology.
- New or updated information will be recorded in the originally completed CRF.
- The investigator will submit any updated SAE data to GSK within the designated reporting time frames.

### 12.3.6. Reporting of SAEs to GSK

#### SAE reporting to GSK via electronic data collection tool

- Primary mechanism for reporting SAEs to GSK will be the electronic data collection tool
- If the electronic system is unavailable for greater than 24 hours, the site will use the paper SAE data collection tool and fax it to the Medical Monitor.
- Site will enter the serious adverse event data into the electronic system as soon as it becomes available.
- The investigator will be required to confirm review of the SAE causality by ticking the 'reviewed' box at the bottom of the eCRF page within 72 hours of submission of the SAE.
- After the study is completed at a given site, the electronic data collection tool (e.g., InForm system) will be taken off-line to prevent the entry of new data or changes to existing data
- If a site receives a report of a new SAE from a study subject or receives updated data on a previously reported SAE after the electronic data collection tool has been taken off-line, the site can report this information on a paper SAE form or to the Medical Monitor by telephone.
- Contacts for SAE receipt can be found at the beginning of this protocol on the Sponsor/Medical Monitor Contact Information page.

**SAE reporting to GSK via paper CRF**

- Facsimile transmission of the SAE paper CRF is the preferred method to transmit this information to the Medical Monitor.
- In rare circumstances and in the absence of facsimile equipment, notification by telephone is acceptable, with a copy of the SAE data collection tool sent by overnight mail
- Initial notification via the telephone does not replace the need for the investigator to complete and sign the SAE CRF pages within the designated reporting time frames.
- Contacts for SAE receipt can be found at this beginning of the protocol on the Sponsor/Medical Monitor Contact Information page.

**SAE reporting to GSK via PIMS**

- Facsimile transmission of the following PIMS listings for the corresponding subject is the preferred method to transmit SAE information to the Medical Monitor:
  - SAE listing
  - Demographic listing
  - Study treatment listing
- In rare circumstances and in the absence of facsimile equipment, notification by telephone is acceptable, with a copy of all required information sent by overnight mail.
- If the PIMS system is unavailable when the SAE occurs, the site will use the paper SAE form and fax that to the Medical Monitor. The site will enter the SAE data into PIMS as soon as the system becomes available.

## 12.4. **Appendix 4: Modified List of Highly Effective Methods for Avoiding Pregnancy in Females of Reproductive Potential (FRP)**

This list does not apply to FRP with same sex partners, when this is their preferred and usual lifestyle or for subjects who are and will continue to be abstinent from penile-vaginal intercourse on a long term and persistent basis.

- Contraceptive subdermal implant
- Intrauterine device or intrauterine system
- Oral Contraceptive, with combined estrogen and progestogen [[Hatcher](#), 2011]
- Injectable progestogen [[Hatcher](#), 2011]
- Contraceptive vaginal ring [[Hatcher](#), 2011]
- Percutaneous contraceptive patches [[Hatcher](#), 2011]
- Male partner sterilization with documentation of azoospermia prior to the female subject's entry into the study, and this male is the sole partner for that subject [[Hatcher](#), 2011].
- Male condom plus partner use of one of the contraceptive options below:
  - Contraceptive subdermal implant
  - Intrauterine device or intrauterine system
  - Oral Contraceptive, either combined or progestogen alone Injectable progestogen [[Hatcher](#), 2011]
  - Contraceptive vaginal ring [[Hatcher](#), 2011]
  - Percutaneous contraceptive patches [[Hatcher](#), 2011]

This is an all inclusive list of those methods that meet the GSK definition of highly effective: having a failure rate of less than 1% per year when used consistently and, correctly and, when applicable, in accordance with the product label. For non-product methods (e.g. male sterility), the investigator determines what is consistent and correct use. The GSK definition is based on the definition provided by the ICH [[ICH, M3 \(R2\)](#) 2009].

The investigator is responsible for ensuring that subjects understand how to properly use these methods of contraception.

